#### 4.5 Concomitant Medications/Treatments

Subjects on the trial are allowed to receive all supportive care therapy needed to alleviate symptoms related to CRC or other medical problems at the investigator's discretion. No treatments should be withheld due to a subject's participation in this study. Prophylaxis for infusion-related reactions should be employed per institutional guidelines.

Infusion-related reactions (including anaphylaxis) may occur during the infusion of nivolumab. Infusion-related reactions are also associated with panitumumab treatment, but no prophylaxis measures are suggested. The infusion of nivolumab (and panitumumab) should be administered at a site properly equipped and staffed to manage anaphylaxis should it occur. Monitor subjects during infusion. If anaphylaxis occurs immediately and permanently discontinue administration of the study medication and administer appropriate medical therapy per institutional standards. If a mild or moderate infusion-related reaction occurs, the infusion should be interrupted, or the rate of infusion slowed, and appropriate medical management instituted. Subjects who experienced a prior infusion-related reaction to nivolumab should be pre-medicated for subsequent infusions per institutional standards. Premedication may include acetaminophen, an antihistamine and a corticosteroid.

Brief (up to 7 days) and episodic use of systemic corticosteroids for other general conditions (e.g. pre-medication for radiographic imaging due to IV contrast allergy, COPD exacerbation, poison ivy, etc.) is allowed.

##### 4.5.1 Prophylaxis for acneiform skin rash related to panitumumab therapy

Subjects receiving panitumumab should receive prophylactic management for EGFR-I associated skin toxicity in accordance with the strategies employed in the STEPP and J-STEPP randomized clinical trials. Subjects should be educated thoroughly on avoiding sun exposure as able. If sun avoidance is not possible, subjects should be advised to wear a hat with brim and to cover extremities with non-restrictive UV protectant clothing.

All subjects should be prescribed prophylactic oral tetracycline antibiotic (Doxycycline 100mg PO BID or Minocycline 100mg PO Daily).

Additionally, the following measures are suggested for rash prophylaxis/management:

1. Skin moisturizer applied to face, hands, feet, neck, back and chest both in the morning on rising and evening (bedtime)
2. Sunscreen (PABA Free, UVA and UVB protectant, SPF 25 or higher) applied to potentially sun-exposed areas before going outdoors.
3. Topical steroids (0.5% Hydrocortisone Cream) applied to face, hands, feet, neck, back and chest both in the morning on rising and evening (bedtime)

October 01,,  
2020

Prophylactic management with the above regimen was continued for 20 weeks in the STEPP and J-STEPP studies (or until the development to intolerance to a component of the prophylactic regimen). Treatment with the above regimen can be continued for the duration of panitumumab-containing therapy at the discretion of the treating physician.

While skin toxicity management is employed pre-emptively per the J-STEPP regimen described above, emergent skin toxicity may still occur. Additional measures for the alleviation of emergent skin toxicity grade 2 or higher will be at the discretion of the treating physician. Treatment strategies/agents selected may include higher-potency topical steroids, oral steroids, and additional topical or systemic antibiotics. Grade 3 rash is considered to be at the panitumumab treatment threshold, and panitumumab dose reduction or delay are implemented also at the discretion of the treating physician. Dermatology consultation is recommended for subjects being considered for dose reduction or cessation due to skin toxicity. Referral to dermatologist should also be recommended for grade 3 or 4 toxicity, skin toxicity that is difficult to manage employing the measures above or does not improve within 1-2 weeks, and any skin toxicity that is severely symptomatic or has an uncharacteristic appearance or distribution.

#### 4.5.2 Treatment of Therapy-Related Infusion Reactions

Since nivolumab contains only human immunoglobulin protein sequences, it is unlikely to be immunogenic and induce infusion or hypersensitivity reactions. Panitumumab caused grade 3-4 infusion reactions in <0.5% of subjects. However, if such a reaction were to occur, it might manifest with fever, chills, rigors, headache, rash, pruritus, arthralgias, hypo- or hypertension, bronchospasm, or other symptoms of allergic-like reactions.

All Grade 3 or 4 infusion reactions should be reported as an SAE if criteria are met. Infusion reactions should be graded according to NCI CTCAEv4.03 guidelines.

Treatment recommendations are provided below and may be modified based on local treatment standards and guidelines as appropriate:

**For Grade 1 symptoms during panitumumab infusion:** (Mild reaction; infusion interruption not indicated; intervention not indicated). Remain at bedside and monitor subject until recovery from symptoms. The following prophylactic premedications are recommended for future infusions: diphenhydramine 50 mg (or equivalent) and 325 to 1000 mg acetaminophen at least 30 minutes before additional therapeutic antibody administrations. Decrease the infusion rate of panitumumab to 50% of the original infusion rate.

**For Grade 1 symptoms during nivolumab infusion:** (Mild reaction; infusion interruption not indicated; intervention not indicated). Remain at bedside and

October 01,,  
2020

monitor subject until recovery from symptoms. The following prophylactic premedications are recommended for future infusions: diphenhydramine 50 mg (or equivalent) and 325 to 1000 mg acetaminophen at least 30 minutes before additional nivolumab administrations.

**For Grade 2 symptoms during panitumumab infusion:** (Moderate reaction requires therapy or infusion interruption but responds promptly to symptomatic treatment [eg, antihistamines, non-steroidal anti-inflammatory drugs, narcotics, corticosteroids, bronchodilators, IV fluids]; prophylactic medications indicated for 24 hours).

Stop the panitumumab infusion, begin an IV infusion of normal saline, and treat the subject with diphenhydramine 50 mg IV (or equivalent) and 325 to 1000 mg acetaminophen; remain at bedside and monitor subject until resolution of symptoms. Corticosteroid or bronchodilator therapy may also be administered as appropriate. If the infusion is interrupted, then restart the infusion at 50% of the original infusion rate when symptoms resolve. Monitor subject closely. If symptoms recur, then no further panitumumab will be administered at that visit. Administer diphenhydramine 50 mg IV and remain at bedside and monitor the subject until resolution of symptoms. The amount of study drug infused must be recorded on the electronic case report form (eCRF). The following prophylactic premedications are recommended for future infusions: diphenhydramine 50 mg (or equivalent) and 325 to 1000 mg acetaminophen should be administered at least 30 minutes before additional NVB administrations. If necessary, corticosteroids (recommended dose: up to 25 mg of IV hydrocortisone or equivalent) may be used.

**For Grade 2 symptoms during nivolumab infusion:** (Moderate reaction requires therapy or infusion interruption but responds promptly to symptomatic treatment [eg, antihistamines, non-steroidal anti-inflammatory drugs, narcotics, corticosteroids, bronchodilators, IV fluids]; prophylactic medications indicated for 24 hours).

Stop the nivolumab infusion, begin an IV infusion of normal saline, and treat the subject with diphenhydramine 50 mg IV (or equivalent) and 325 to 1000 mg acetaminophen; remain at bedside and monitor subject until resolution of symptoms. Corticosteroid or bronchodilator therapy may also be administered as appropriate. If the infusion is interrupted, then restart the infusion at 50% of the original infusion rate when symptoms resolve; if no further complications ensue after 30 minutes, the rate may be increased to 100% of the original infusion rate. Monitor subject closely. If symptoms recur, then no further nivolumab will be administered at that visit. Administer diphenhydramine 50 mg IV and remain at bedside and monitor the subject until resolution of symptoms. The amount of study drug infused must be recorded on the electronic case report form (eCRF). The following prophylactic premedications are recommended for future infusions: diphenhydramine 50 mg (or equivalent) and 325 to 1000 mg (acetaminophen)

should be administered at least 30 minutes before additional NVB administrations. If necessary, corticosteroids (recommended dose: up to 25 mg of IV hydrocortisone or equivalent) may be used.

**For Grade 3 or Grade 4 symptoms of panitumumab or nivolumab:** (Severe reaction, Grade 3: prolonged [ie, not rapidly responsive to symptomatic medication and/or brief interruption of infusion]; recurrence of symptoms following initial improvement; hospitalization indicated for other clinical sequelae [eg, renal impairment, pulmonary infiltrates]). Grade 4: (life threatening; pressor or ventilatory support indicated).

Immediately discontinue infusion of the therapeutic antibody. Begin an IV infusion of normal saline and treat the subject as follows. Recommend bronchodilators, epinephrine 0.2 to 1 mg of a 1:1,000 solution for subcutaneous administration or 0.1 to 0.25 mg of a 1:10,000 solution injected slowly for IV administration, and/or diphenhydramine 50 mg IV with methylprednisolone 100 mg IV (or equivalent), as needed. Subject should be monitored until the investigator is comfortable that the symptoms will not recur. The offending therapeutic antibody will be permanently discontinued. Investigators should follow their institutional guidelines for the treatment of anaphylaxis. Remain at bedside and monitor subject until recovery from symptoms.

In the case of late-occurring hypersensitivity symptoms (eg, appearance of a localized or generalized pruritus within 1 week after treatment), symptomatic treatment may be given (eg, oral antihistamine, or corticosteroids).

#### 4.5.3 Special warnings and precautions

- Nivolumab and ipilimumab are associated with immune-related AEs. Subjects should be monitored continuously (at least up to 5 months after the last dose) as an AE with nivolumab/ipilimumab may occur at any time during or after discontinuation of therapy.
- For suspected immune-related reactions, adequate evaluation should be performed to confirm etiology or exclude other causes. Based on the severity of the adverse reaction, nivolumab/ipilimumab should be withheld and corticosteroids administered. If immunosuppression with corticosteroids is used to treat an AE, a taper of at least 1-month duration should be initiated upon improvement. Rapid tapering may lead to worsening of the AE. Non-corticosteroid immunosuppressive therapy should be added if there is worsening or no improvement despite corticosteroid use.

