3. The end of treatment visit should only occur when subjects permanently stop study treatment. Subjects who have an ongoing  $\geq$  grade 2 or serious AE (SAE) at this visit will continue to be followed until the event is resolved or deemed irreversible by the investigator. The 30-day (+/- 7 days) follow up visit after stopping study treatment should be performed to check for ongoing toxicity. Subsequently, subjects should be contacted by telephone at approximately 100 days (+/- 7 days) after discontinuing study treatment for the emergence of SAEs (including checking for pregnancy) and to ensure contraceptive guidelines are followed as stipulated in inclusion criteria 3.1.11 and 3.1.12. Subsequent long-term follow-up for survival, defined as every 90 days thereafter (+/- 15 days) for up to 3 years or until death (whichever is first) may be conducted via telephone or chart review and/or clinic visit. Long term survival follow up will be limited to history of any subsequent cancer treatments, an assessment of any SAEs (including checking for pregnancy) considered to be possibly or probably related to study treatment until resolution, and survival status.
4. Complete history at baseline only, thereafter focused history on symptoms/toxicity; physical exam to include height (baseline only), examination of the skin, weight, and vital signs. Note that starting with cycle 7, only include assessment by physician on days 15 and 29 if clinical signs and symptoms warrant MD consult
5. Tumor imaging should remain consistent throughout study and should include those thought by investigator to best capture status of disease. Disease assessments should include contrasted computed tomography (CT) of the chest and either contrasted CT of abdomen and pelvis or MRI of abdomen and pelvis. Repeat tumor imaging every 12 weeks (+/- 1 week).
6. Urine or serum  $\beta$ -HCG must be performed within 24 hours prior to first dose of study medication for women of child-bearing potential. The test result must be confirmed as negative prior to dosing with study medication. A serum or urine pregnancy test must be repeated every 6 weeks while receiving study medications and repeated approximately 30 days after discontinuing the study medications.

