## **7.2 Documentation of non-serious AEs or SARs**

For non-serious AEs or SARs, documentation must begin from day 1 of study treatment and continue through the 100-day follow-up period after treatment is discontinued.

Collected information should be recorded in the electronic Case Report Forms (eCRF) for that subject. Please include a description of the event, its severity or toxicity grade, onset and resolved dates (if applicable), and the relationship to the study drug. Documentation should occur at least monthly.

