## **7.3 SAEs or Serious SARs**

### **7.3.1 Timing**

After informed consent but prior to initiation of study medications, only SAEs caused by a protocol-mandated intervention will be collected (e.g. SAEs related to invasive procedures such as biopsies, medication washout).

For any other experience or condition that meets the definition of an SAE or a serious SAR, recording of the event must begin from day 1 of study treatment and continue through the 100-day follow-up period after treatment is discontinued.

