##### Pregnancy

Pregnancies and suspected pregnancies (including a positive pregnancy test regardless of age or disease state) of a female subject or a female partner of a male subject occurring while the subject is on study, or within the period stipulated for continued contraceptive use for WOCBP (5 months) and sexually active men (6 months) after the subject's last dose of study medication should be recorded as SAEs. The female subject is to be discontinued immediately from the study for a pregnancy event.

For Affiliate sites, the pregnancy, suspected pregnancy, or positive pregnancy test must be reported to the Multicenter Project Manager immediately (within 24 hours) at [contact] (primary route of submission) or [contact] (back-up)). The Multicenter Project Manager will then report the event to the Funding Source (see requirements below). The female subject or the female partner of a male subject should be referred to an obstetrician-gynecologist, preferably one experienced in reproductive toxicity for further evaluation and counseling.

The Investigator will follow the female subject or female partner of a male subject until completion of the pregnancy, and must document the outcome of the pregnancy (either normal or abnormal outcome) and report the condition of the fetus or newborn to the Multicenter Project Manager. If the outcome of the pregnancy was abnormal (e.g., spontaneous or therapeutic abortion), the Investigator should report the abnormal outcome as an AE. If the abnormal outcome meets any of the serious criteria, it must be reported as an SAE.

Note if the female subject or female partner of a male subject has received nivolumab, the investigator must immediately notify Worldwide Safety @BMS of this event via the Pregnancy Surveillance Form in accordance with SAE reporting procedures. The nivolumab IB notes that non-clinical safety findings of adverse pregnancy outcomes and infant losses in the absence of maternal toxicity have been reported. Findings in monkeys suggest a potential risk to human pregnancy if there is continued treatment with nivolumab during pregnancy.

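### Immune-related monitoring is set at 5 months or more after the last dose, but new non-serious events have no recording rule after day 100, and the rule for new related SAEs is inconsistent

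*Combined protocol and SAP*

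**What the plan says.** - **Monitoring period.** Section 4.5.3 says of nivolumab and ipilimumab: "Subjects should be monitored continuously (at least up to 5 months after the last dose". Its reason is that an AE may arise at any time during treatment or after it stops.
- **Recording period.** For non-serious events, Section 7.2 says "documentation must begin from day 1 of study treatment and continue through the 100-day follow-up period after treatment is discontinued". For SAEs, Section 7.3.1 says "recording of the event must begin from day 1 of study treatment and continue through the 100-day follow-up period after treatment is discontinued".
- **Contacts.** Under footnote 3 of the Section 6.1 table, "subjects should be contacted by telephone at approximately 100 days (+/- 7 days) after discontinuing study treatment for the emergence of SAEs". Long-term follow-up then comes at intervals "defined as every 90 days thereafter (+/- 15 days) for up to 3 years or until death".
- **Content of long-term contacts.** Footnote 3 opens its list of permitted content with "Long term survival follow up will be limited to history of any subsequent cancer treatments". The remaining items in that list are "an assessment of any SAEs (including checking for pregnancy) considered to be possibly or probably related to study treatment until resolution, and survival status". Section 6.4.4 says much the same. The Toxicity Assessment row of the table is marked in all 14 columns, including long-term follow-up.
- **Pregnancy.** Section 7.3.3 treats a pregnancy as an SAE to be recorded during the study and also "within the period stipulated for continued contraceptive use for WOCBP (5 months) and sexually active men (6 months", counting from the final dose.
- **Concomitant medication.** The last scheduled collection is the 30-day visit (Sections 6.1 and 6.4.2).

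**The concern.** The protocol names late immune-related events as a risk and gives a minimum period for watching for them, but its recording rules stop earlier. Monitoring that leaves no record cannot inform the safety objective.

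Objective 2.2.6 and Section 8.4 count treatment-emergent toxicities by grade (Grade 3 and 4). Seriousness in Section 7.1.4 depends mainly on outcome, such as admission for more than 24 hours, and not on grade. A Grade 3 rash managed as an outpatient at month 4 could therefore belong in the safety summary without being an SAE, and after day 100 nothing requires a site to enter it. Corticosteroids started for it would not be collected on schedule either.

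**Working it through.** There is no sample-size or error-rate figure to reproduce. The check is calendar arithmetic plus a comparison of the rules.

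**1. Length of the uncovered span.** Inputs: at least 5 months (4.5.3) and 100 days (7.2, 7.3.1).
- 5 months = 5 × 365.25 / 12 = 152.2 days.
- 152.2 − 100 = 52.2 days, and 52.2 / 152.2 = 34%.
- This assumes that discontinuation is dated on the day of the last dose.

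**2. Effect of the two clocks.** Section 4.5.3 counts from the last dose; 7.2 and 7.3.1 count from discontinuation. Section 4.4.2.3.1 allows delays of up to 42 days before permanent discontinuation.
- Discontinuation dated 42 days after the last dose: 100 + 42 = day 142, leaving 152 − 142 = about 10 days.
- If the 42 days run from a missed two-weekly dose: 100 + 14 + 42 = day 156, so no shortfall remains.
- The shortfall therefore ranges from about 52 days down to nil.

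**3. Contact schedule, in days after discontinuation.**
- 100-day call: 100 ± 7 = days 93 to 107.
- First long-term contact: 100 + 90 ± 15 = days 175 to 205.
- Gap between the nominal windows: 175 − 107 = 68 days.
- If the 90 days run from the actual call: days 168 to 198 after a day-93 call, or 182 to 212 after a day-107 call.
- With both clocks starting together, month 5 (day 152) falls inside the gap. The first contact after it comes 168 − 152 = 16 to 212 − 152 = 60 days later.

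**4. What applies to an event that starts after day 100.**

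| Event | Recording rule (7.2, 7.3) | Long-term contact (footnote 3, 6.4.4) | Result |
|---|---|---|---|
| Non-serious immune-related AE | None after day 100 | Not in the listed content | No rule |
| Related SAE | None in 7.3.1 after day 100 | Assessed, followed to resolution | Inconsistent |
| Pregnancy | 5 or 6 months (7.3.3) | Checked (footnote 3) | Covered; 7.3.1 does not say so |

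The related-SAE row is unclear because the wording about resolution can mean either SAEs already open or any related SAE found at the contact. On the wider reading, an event at month 4 or 5 would be picked up retrospectively at about day 190.

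**The case against.** The strongest defence is that 4.5.3 is a clinical precaution and not a data rule, so a recording window shorter than the period of vigilance is a legitimate design choice. The schedule also offers more than 7.2 and 7.3.1 suggest:
- Related SAEs are assessed every 90 days for up to 3 years, and the toxicity row is marked throughout.
- Section 6.4.3 makes the 100-day contact a CTCAE toxicity evaluation.
- Subjects with a Grade 3 or 4 event or SAE during treatment are contacted every 2 weeks until it resolves, and such contacts can reveal new events.
- Section 7.1.4 treats important medical events and potential drug-induced liver injury as serious, so a late hepatitis may well be an SAE.
- Section 8.4 gives no post-treatment window for treatment-emergent events, so events at months 4 and 5 are not certain to belong in the summary.

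Much of this stands. It defeats the inference, which a reader might draw from 7.2 and 7.3.1 alone, that all safety recording stops at 100 days and late immune-related events go unrecorded. It also defeats the inference that footnote 3 confines the 100-day call to SAEs, since 6.4.3 and 7.2 ask for more.

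It does not close the gap for non-serious events. Footnote 3 and 6.4.4 restrict the long-term content despite the mark in the table. The 2-weekly contacts reach only subjects with an earlier severe event, and only until that event resolves. If the shorter window was a deliberate choice, the protocol gives no reason for it and leaves 7.3.1 at odds with footnote 3.

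**Conclusion.** The point holds in a limited form. New non-serious immune-related AEs starting after day 100, Grade 3 included, have no recording rule for up to about 52 of the 152 days in the protocol's own minimum monitoring period. For new related SAEs after day 100 the sections disagree. The 52 days assume that discontinuation and last dose coincide; a dosing hold shortens the span and can remove it.

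Three stronger readings are not supported:
- **A third of late events are missed.** The 34% counts calendar days. The documents give no distribution of onset times, so the number of missed events cannot be estimated.
- **The Grade 3 and 4 summary loses Grade 2 events.** Those never enter it. Only new non-serious Grade 3 or 4 events are at stake.
- **The pregnancy rules contradict each other outright.** Section 7.3.3 is a specific rule extending a general one, and footnote 3 checks for pregnancy. A cross-reference is enough.

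The primary endpoint is unaffected. The toxicity boundary in Section 8.3 counts events that call for stopping therapy, so events first arising months after therapy ended bear little on it. The effect is on how completely the secondary safety objective is described, which justifies an inexpensive correction.

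**What to change.** 1. Reconcile Sections 4.5.3, 6.1 (table and footnote 3), 6.4.3, 6.4.4, 7.2, 7.3.1 and 7.3.3 on one clock, the last dose.
2. In 7.2 and 7.3.1, align the recording window for immune-related AEs of any seriousness, and for related SAEs, with the 5 months in 4.5.3. Say explicitly that new events count, as well as those already open.
3. State in 7.3.1 that pregnancies follow the 7.3.3 window.
4. Move the first long-term telephone contact so that its window opens at or after month 5, for example days 155 to 170 after the last dose. A window of day 150 ± 15 would not do, because a call on day 135 would come 152 − 135 = 17 days too early. The call should ask about new immune-related AEs and any immunosuppressant started.
5. Keep a pregnancy check at or after 6 months (6 × 365.25 / 12 = about day 183). If 90 ± 15 day spacing follows the moved call, the next contact falls between 155 + 75 = day 230 and 170 + 105 = day 275 and can carry it. If a check nearer 6 months is wanted, keep the present contact at about day 190 and add one short call.

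The cost is protocol wording, a change to the eCRF window and a few more AE entries. A planned telephone call moves earlier, and no clinic visit is added. Dosing and the management of toxicity are untouched.
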